#### 5.8 Subgroup analyses

No subgroup analysis will be conducted.

#### 5.9 Interim Analyses

After all study participants complete the week 16 visit, a final Week 16 analysis will be authorization performed. A final analysis and final CSR will also be prepared once all data (through the SFU visit for study participants not entering the MAP) have been collected.

#### 5.10 Data Monitoring Committee (DMC) or Other Review Board

No Data Monitoring Committee will be conducted.

#### SUPPORTING DOCUMENTATION 6

#### 6.1 Appendix 1 Additional analysis specifications

#### 6.1.1 Baseline characteristics and demographics

All summaries detailed in this section will be performed on the RS by treatment group. Summaries for demographics and other baseline characteristics will also be repeated on SS. If the RS and SS analysis sets are identical, the SS summary will not be produced,

#### 6.1.1.1 **Demographics**

Demographic variables will be summarized by treatment group and overall.

Led to and maxin The following continuous variables will be summarized using descriptive statistics (number of study participants, mean, SD, minimum, median and maximum).

- Age at the time of study entry (years)
- Height (cm)
- Weight (kg)
- BMI  $(kg/m^2)$

BMI  $(kg/m^2)$  will be calculated as:

$$BMI = \frac{Weight (kg)}{(Height (m))^2}$$

The following categorical variables will be summarized using frequency counts and percentages.

- Age group (18- $<65, 65-<85, \geq 85$  years)
- Age group ( $\leq 18, 19 \langle 65, \geq 65 \rangle$  years)
- Age group ( $<40, 40-<65, \ge 65$  years)
- Body weight ( $\leq 100 \text{ kg}$ , >100 kg)
- Body Weight ( $\leq 120 \text{ kg}$ , >120 kg)
- Gender
- Race
- Ethnicity
- BMI (<25 kg/m2, 25 to <30 kg/m2,  $\geq 30 \text{ kg/m2}$ )

By-study participant listings of demographics for all study participants screened will be provided.

#### 6.1.1.2 Other baseline characteristics

Baseline characteristics will be summarized by dose group and overall including but not limited to:

- constant and a line the the second of the se PSO history parameters including duration of disease, calculated as date of randomization -• date of PSO first diagnosis
- PSO BSA (%)
- PASI score •
- PASI score ( $<20, \geq 20$ )
- DLQI total score •
- DLQI total score (=0, >0) •
- PSD items: Pain, Itch, Scaling •
- Duration of disease (<median, ≥median) ٠
- IGA score ٠
- Scalp involvement (yes, no) •
- PHQ-9 total score •
- Prior biologic therapy (Yes, No, Missing) ٠
- Prior primary failure to biologic (Yes, No, Missing) •
- Prior anti-TNF therapy (Yes, No, Missing) •
- Prior phototherapy or chemotherapy (Yes, No, Missing) •
- Any prior systemic therapy (Yes, No, Missing)

Baseline scalp involvement is based on the number of participants achieving scalp IGA>0.

If the date of onset of plaque PSO is partial, it should be imputed to the most recent feasible date (ie, last day of the month if only day is missing, or the last day of the year if day and month are missing). If the date of randomization is missing, then the duration of disease will be derived using the date of Screening.

Continuous variables will be summarized descriptively. Categorical variables will be summarized using frequency counts and percentages.

#### 6.1.2 Protocol deviations

A summary, using the RS, displaying the number and percentage of study participants with an important protocol deviation (including a summary of study participants excluded from the PPS or PK-PPS due to important protocol deviations) by treatment group will be provided.

Important protocol deviations will be categorized as follows:

- Inclusion criteria deviation
- Exclusion criteria deviation
- Incorrect treatment or dose
- Treatment noncompliance
- Withdrawal criteria deviation
- Procedural noncompliance
- Prohibited concomitant medication use

A by-study participant listing of important protocol deviations will be provided.

authorization The impact on study conduct of the Coronavirus Disease 2019 (COVID-19) global pandemic will be assessed and captured as: confirmed COVID-19 infection, suspected COVID-19 infection, general circumstances around COVID-19 without infection or any other deviation from the protocol due to COVID-19.

#### Medical history and concomitant diseases 6.1.3

Previous and ongoing medical history will be summarized by dose group for the RS by SOC and PT using MedDRA version 19.0. Medical procedures are not coded.

The following listings for medical history and concomitant diseases will be provided: medical history, psoriasis history, concomitant medical procedures, previous and ongoing medical history glossary, previous and ongoing medical history conditions, and procedure history.

#### Prior/concomitant/follow-up medications 6.1.4

Medication start and stop dates will be compared to the date of first dose of treatment to allow medications to be classified as either Prior or Concomitant. Detailed information of imputation methods for missing or partial dates could be found in 5.1.1.7.3.

Prior medications include any medications that started prior to the start date of study medication.

Concomitant medications are medications taken at least one day in common with the study medication dosing period, which the dosing period starts from the date of first dose to the date of last dose plus 28 days.

The number and percentage of study participants taking prior medications will be summarized by treatment group, overall and by Anatomical Therapeutic Chemical classification (ATC) class, presenting Anatomical Main Group (ATC Level 1), Pharmacological Subgroup (ATC level 3), and preferred term. The number and percentage taking concomitant medications will be summarized similarly.

Past psoriasis medications will be captured separately and will also be summarized by treatment group. These medications are not subject to dictionary coding. In addition, study participants who failed past psoriasis biologic treatment will be summarized by reason of failure as captured on the Psoriasis Treatment History CRF module.

By-study participant listings of all Prior and Concomitant medications, prior and concomitant medications glossary will be provided.

Bimekizumab

The number and percentage of study participants with concomitant vaccines for COVID-19 will be summarized by treatment group, overall and by World Health Organization Drug Dictionary Standardised Drug Grouping (SDG), presenting SDG subgroup, and preferred term. The SDG subgroup Vaccines for COVID-19 will be used to identify vaccines for COVID-19 using the narrow scope; this subgroup is divided further into separate subgroups which is the level that will be presented. The number of individual occurrences of the vaccine for COVID-19 will also be summarized.

A by-study participant listing of all Concomitant vaccines for COVID-19 will be provided.

# 6.1.5 Data derivation rules

# 6.1.5.1 PASI

The PASI scoring of psoriatic plaques is based on three criteria: redness (R), thickness (T), and scaliness (S). Severity is rated for each index (R, S, T) on a 0 to 4 scale (0 for no involvement up to 4 for very marked involvement). The body is divided into 4 areas comprising the head (h), upper extremities (u), trunk (t), and lower extremities (l). In each of these areas, the fraction of total surface area affected is graded on a 0-6 scale (0 for no involvement; up to 6 for 90% - 100% involvement).

The various body regions are weighted to reflect their respective proportion of BSA. The composite PASI score is then calculated by multiplying the sum of the individual-severity scores for each area by the weighted area-of-involvement score for that respective area, and then summing the four resulting quantities as follows (note for R, T, and S scores are as follows: 0 =one, 1 =slight, 2 = moderate, 3 = marked, and 4 = very marked):

$$PASI = (0.1 \times (R_h + T_h + S_h) \times A_h) + (0.2 \times (R_u + T_u + S_u) \times A_u) + (0.3 \times (R_t + T_t + S_t) \times A_t) + (0.4 \times (R_l + T_l + S_l) \times A_l)$$

where

 $R_h$ ,  $R_u$ ,  $R_t$ ,  $R_l$  = redness score of plaques on the head, upper extremities, trunk, and lower extremities, scored 0-4 respectively;

 $T_h$ ,  $T_u$ ,  $T_t$ ,  $T_l$  = thickness score of plaques on the head, upper extremities, trunk, and lower extremities, scored 0-4 respectively;

 $S_h$ ,  $S_u$ ,  $S_t$ ,  $S_l$  = scaliness score of plaques on the head, upper extremities, trunk, and lower extremities, scored 0-4 respectively;

A_h, A_u, A_t, A_l = numerical value translation of % area of psoriatic involvement score for the head, upper extremities, trunk, and lower extremities, respectively (where 0 = 0% [clear], 1 = >0% to <10%, 2 = 10% to <30%, 3 = 30% to <50%, 4 = 50% to <70%, 5 = 70% to <90%, and 6 = 90% to 100%).

The highest potential PASI score is 72 for severe disease; the lowest is 0 for no psoriasis lesions. PASI scores are treated as continuous. The percent improvement in PASI scores from Baseline will be computed as:

 $Percent\ Improvement\ from\ Baseline\ =\ 100\times \frac{Baseline\ PASI\ -\ Post\ Baseline\ Timepoint\ PASI\ Baseline\ PASI\ }{Baseline\ PASI\ }$ 

Bimekizumab

If a study participant has experienced an improvement, this measure will be positive. If a study participant has experienced a worsening in their condition, this measure will be negative.

If a study participant is missing 1 or 2 severity measurements for a certain region, the average of the remaining severity measurement(s) within that region will be utilized to substitute for the missing severity measurement(s) in that region. If the area of affected skin and/or all severity measurements for up to 2 regions are missing, then the missing (R+T+S) x A for a region will be substituted by the average of the available (R+T+S) x A. Otherwise, the PASI will be set to missing.

# 6.1.5.2 Exposure-adjusted rates

The EAIR is defined as the number of study participants (n) with a specific AE adjusted for the exposure and will be scaled to 100 participant-years:

$$EAIR = 100 \times n / \sum_{i=1}^{N} (T_{\text{Exp}(i)})$$

Where  $T_{\text{Exp}(i)}$  is the exposure time for the ith participant and N is the number of participants at risk.

If a study participant has multiple events, the time of exposure is calculated to the first occurrence of the AE being considered. If a study participant has no events, the total time at risk is used. Exact Poisson 95% confidence intervals for incidence rates are calculated using the relationship between the Poisson and the Chi-square distribution (Ulm, 1990; Fay and Feuer, 1997):

$$LCL = \chi_{2n,\alpha/2}^2 / 2$$
$$UCL = \chi_{2(n+1),1-\alpha/2}^2 / 2$$

where n is the number of participants with a specific AE for the incidence rate of interest and is the basis for the number of the degrees of freedom for the chi-square quantile for the upper tail probability  $\chi^2$ .

The EAER will be the number of AEs including repeat occurrences in individual participants divided by the total time at risk scaled to 100 participant-years and calculated using:

$$EAER = 100 \times N_{AE} / \sum_{i=1}^{N} (T_{\text{Risk}(i)})$$

where  $N_{AE}$  is the total number of AEs,  $T_{Risk(i)}$  is the time at risk for then ith participant, and N is the total number of participants at risk.

No confidence interval will be computed for EAER.

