5.6.1 Extent of Exposure

Summaries for exposure will be provided. This consists of a descriptive summary of study medication duration in days. In addition, total study medication duration and time at risk will be

5.6

summarized in years by treatment group. The cumulative study medication duration will be summarized for study participants exposed for given durations of time, with four weekly categories through Week 16: izzation

- >0 week
- >4 weeks
- >8 weeks
- ≥ 12 weeks
- >16 weeks

Definitions for study medication duration (days) during the Treatment Period are provided as follows: s eleo

Study medication duration (days):

- Date of last dose - date of first dose + 28 days

The use of +28 days reflects the dosing interval of Q4W.

Note: For participants who died during the treatment period, the calculation reverts to:

- Date of death – date of first dose + 1

Time at Risk (Days) during the Treatment Period:

For study participants who complete the final visit (week 16) of the Treatment Period:

• Date of Week 16 visit – Date of first dose +1

For study participants who discontinue on or prior to the final visit of the Treatment Period, use the minimum of the following:

- Planned total number of days in the Treatment Period (112 days)
- Date of last clinical contact Date of first dose +1

For study participants who died during the Treatment Period:

Date of death – date of first dose +1

Date of last clinical contact for each study participant in the Treatment Period is defined as the maximum of last visit date in the Treatment Period, last imputed AE start date, date of study termination or completion, last date of study drug administration.

Time at Risk (Days) during the Treatment Period + SFU:

For study participants who complete the final visit (week 16) of the Treatment Period and enter the MAP:

Date of Week 16 visit – Date of first dose +1

For study participants who do not enter the MAP, use the minimum of the following:

- Date of last dose Date of first dose +141
- Date of last clinical contact Date of first dose +1

For study participants who died prior to the end of time at risk as defined above:

Date of death - date of first dose +1

Date of last clinical contact for each study participant in the Treatment Period + SFU is defined as the maximum of: last visit date including SFU, last imputed AE start date, date of study termination or completion, last date of study drug administration.

5.6.2 **Adverse Events**

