ion An AE is any untoward medical occurrence in a subject or clinical investigation subject administered a pharmaceutical product that does not necessarily have a causal relationship with this treatment. An AE can therefore be any unfavorable and unintended sign (including an abnormal laboratory finding), symptom, or disease temporally associated with the use of a medicinal (investigational) product, whether or not related to the medicinal (investigational) product. Adverse events will be coded according to the Medical Dictionary for Regulatory Activities (MedDRA version 19.0).

5.6.2.1 **Data considerations**

Treatment-emergent AEs are defined as those AEs that have a start date on or following the first dose of IMP through the to the end of the time at risk, as defined in section 5.6.

The rules for imputing partial start or stop dates are outlined in 5.1.1.7.3. If it is not possible (due to partial dates) to determine whether an AE is treatment-emergent then it will be assumed to be a TEAE. If the intensity of an AE is unknown, it will be considered as severe. If the relationship to study drug is missing, it will be considered as related.

Treatment-emergent AEs will be summarized as study participant incidence (number and percentage of study participants experiencing the AE) and AE frequencies (number of AEs including repeat events) by treatment group.

Selected AE summaries will include the exposure-adjusted incidence rate (EAIR) and the exposure-adjusted event rate (EAER). The 95% CIs will be reported for the EAIR only.

The EAIR is the total number of study participants with a specific AE divided by the total time at risk across all study participants. If a study participant has multiple events, the time of exposure is calculated to the first occurrence of the AE being considered. If a study participant has no events, the total time at risk is used. The EAER is the total number of AEs including repeat occurrences in individual study participants divided by the total time at risk across all study participants. Exposure adjusted rates (EAIR and EAER) will be scaled to 100 participant-years. Study participant time at risk represents the time a participant is at risk for having an AE. These definitions will be used in calculations of exposure-adjusted rates for adverse events.

Details of the calculations for exposure adjusted rates (EAIR and EAER) can be found in section 6.1.5.2

The following PTs will be used to classify COVID-19 adverse events:

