5.6.2.2 AE Summaries

The AE summaries listed below will be provided based on incidence during the Treatment Period.

The following summaries will be provided by treatment group. In addition, all summaries of TEAEs based on "100 subject years" will include EAIR (with 95% confidence interval) and EAER.

- Incidence of TEAEs Overview
- Incidence of TEAEs per 100 subject years by SOC, HLT, and PT
- Incidence of Serious TEAEs per 100 subject years by SOC, HLT, and PT
- Incidence of TEAEs Leading to Discontinuation per 100 subject years by SOC, HLT, and PT
- Incidence of TEAEs Leading to Death by SOC, HLT, and PT
- Incidence of TEAEs by Maximum Relationship by SOC, HLT, and PT
- Incidence of COVID-19 TEAEs by SOC, HLT, and PT
- Incidence of TEAEs by during and post COVID-19 pandemic by SOC, HLT, and PT (if applicable, see section 5.2.1)
- Incidence of Related Serious TEAEs by SOC, HLT, and PT
- Incidence of TEAEs by Maximum Intensity, SOC, HLT, and PT
- Incidence of TEAEs by decreasing frequency of PT
- Incidence of Non-Serious TEAEs by SOC, HLT, and PT
- Incidence of Non-Serious TEAEs by Maximum Relationship SOC, HLT, and PT
- Incidence of Non-Serious TEAEs Above Reporting Threshold of 5% by SOC and PT
- Incidence of Serious TEAEs by Relationship SOC and PT
- Incidence of Related TEAEs by SOC, HLT, and PT
- Incidence of TEAEs per 100 subject years by SOC, HLT, and PT and by Time of Onset Relative to Anti-bimekizumab Antibody Status (subjects treated with BKZ)
- Incidence of TEAEs per 100 subject years by SOC, HLT, and PT and by Time of Onset Relative to Neutralizing Anti-bimekizumab Antibody Status (subjects treated with BKZ)

In addition, the AE summaries listed below will be provided based on the incidence in the Treatment + SFU Period.

- Incidence of TEAEs Overview
- Incidence of TEAEs per 100 subject years by SOC, HLT, and PT
- Incidence of Serious TEAEs per 100 subject years by SOC, HLT, and PT
- Incidence of TEAEs Leading to Discontinuation per 100 subject years by SOC, HLT, and PT
- Incidence of TEAEs Leading to Death by SOC, HLT, and PT

A by-study participant listing of TEAEs which code to the "Infections and Infestations" SOC and Emerged within 30 days of when a CTCAE Grade 3 or 4 Neutrophil Value Occurred will be presented.

The AE summaries listed below will be provided to assess the impact of COVID-19 mass vaccination on TEAEs through the Treatment Period.

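### The SAP's 95% CI for the exposure-adjusted incidence rate is on the event-count scale: exposure and the factor of 100 are missing from both limits.

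*SAP*

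**What the plan says.** SAP 6.1.5.2 defines the EAIR as 100 × n / ΣT_Exp, where n is the number of participants with the event. The rate is "adjusted for the exposure and will be scaled to 100 participant-years", and each affected participant's exposure stops at the first occurrence. The same section then says: "Exact Poisson 95% confidence intervals for incidence rates are calculated using the relationship between the Poisson and the Chi-square distribution". It gives the lower limit as "LCL = \chi_{2n,\alpha/2}^2 / 2" and the upper limit as the chi-square quantile with 2(n+1) degrees of freedom and subscript 1−α/2, also halved. The explanatory text under the limits defines only n and the quantile; it refers to the "degrees of freedom for the chi-square quantile for the upper tail" probability.

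SAP 5.6.2.1 sets the scale: "Exposure adjusted rates (EAIR and EAER) will be scaled to 100 participant-years". It adds: "The 95% CIs will be reported for the EAIR only". It refers to 6.1.5.2 for the details of the calculation. SAP 5.6.2.2 says the summaries per 100 subject-years "will include EAIR (with 95% confidence interval) and EAER".

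**The concern.** The estimate carries exposure and a factor of 100, but its confidence limits carry neither. As printed, they bound the expected number of participants with the event, not a rate per 100 participant-years. Two arms with the same n would get identical intervals, although 2:1 allocation gives them roughly 2:1 exposure.

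At stake is the CI column in the tables per 100 subject-years: all TEAEs, serious TEAEs, TEAEs leading to discontinuation, and TEAEs by antibody status. The first three correspond to the secondary safety endpoints. Because 6.1.5.2 is the section that specifies the calculation, a programmer and an independent validator who both follow it would agree on the same wrong limits.

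**Working it through.** The documents contain no numerical EAIR or interval to reproduce, so the check evaluates the formulas. No expected event counts are given either, so n is assumed and shown over a range.

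**Inputs**
- Arm sizes: 30 bimekizumab, 15 placebo (SAP 3).
- Treatment Period: 112 days planned (SAP 5.6.1).
- Treatment + SFU, participants not entering the MAP: up to last dose − first dose + 141 days (SAP 5.6.1). The last dosing visit is Week 12 (SAP 6.1.10), so 84 + 141 = 225 days.
- α = 0.05, two-sided.

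**What the printed limits are.** Read as lower-tail quantiles, L(n) = χ²(2n, 0.025)/2 and U(n) = χ²(2(n+1), 0.975)/2. For n = 1, 3, 5 and 10, the Poisson tail probabilities P(X ≥ n | L) and P(X ≤ n | U) both equal 0.025. These are therefore the exact 95% limits for a Poisson mean count.

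**The missing factor** is 100/ΣT_Exp, which equals 1 only at exactly 100 participant-years (PY).
- Bimekizumab, Treatment Period: 30 × 112/365.25 = 9.20 PY; 100/9.20 = 10.9
- Placebo, Treatment Period: 15 × 112/365.25 = 4.60 PY; 100/4.60 = 21.7
- Bimekizumab, Treatment + SFU, no MAP entry: 30 × 225/365.25 = 18.48 PY; factor 5.4
- Placebo, Treatment + SFU, no MAP entry: 15 × 225/365.25 = 9.24 PY; factor 10.8

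**Treatment Period, everyone followed for 112 days**

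| n | Limits as printed (either arm) | Bimekizumab EAIR (correct limits) | Placebo EAIR (correct limits) |
|---|---|---|---|
| 1 | 0.03 to 5.57 | 10.9 (0.3 to 60.6) | 21.7 (0.6 to 121.1) |
| 3 | 0.62 to 8.77 | 32.6 (6.7 to 95.3) | 65.2 (13.5 to 190.6) |
| 5 | 1.62 to 11.67 | 54.4 (17.6 to 126.8) | 108.7 (35.3 to 253.7) |
| 10 | 4.80 to 18.39 | 108.7 (52.1 to 199.9) | 217.4 (104.3 to 399.8) |

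**Does the printed interval contain its own estimate?** In the Treatment Period the EAIR lies above the printed upper limit for every n from 1 to 30 (bimekizumab) and from 1 to 15 (placebo). In Treatment + SFU with full follow-up there is one exception, bimekizumab n = 1: EAIR 5.41 against an upper limit of 5.57, where the correct limits are 0.1 to 30.1.

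**Effect of stopping exposure at the first event.** This shortens ΣT_Exp and enlarges the missing factor. For bimekizumab n = 5:
- All five events at mid-period: 8.43 PY, EAIR 59.3, correct limits 19.3 to 138.4.
- All five on Day 1: (25 × 112 + 5)/365.25 = 7.68 PY, EAIR 65.1, correct limits 21.1 to 151.9.

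**Tail wording.** A literal upper-tail reading of the printed subscripts reverses the limits: for n = 5 the lower limit becomes 10.24 and the upper 2.20. The subscripts work only as lower-tail probabilities.

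**The case against.** The strongest reply is that this is an unfinished specification, not a wrong method. The exact Poisson approach is standard, the printed expressions are its correct first step, and the text says the intervals are for incidence rates. With the scale fixed in SAP 5.6.2.1 and the CI attached to the EAIR in 5.6.2.2, a competent programmer would probably divide by exposure. If not, an interval that excludes its own estimate would stand out in table review. The intervals are also descriptive. Protocol 9.4.1.1 plans numbers, percentages and event counts and leaves further detail to the SAP, so no hypothesis or decision rests on them.

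Much of this stands. The method is sound, the intended scale can be inferred, and the consequence arises only if the formulas are followed literally. The corrected intervals above are also illustrations under assumed counts and full planned follow-up. Even the single Treatment + SFU exception disappears if that event falls on Day 1: (29 × 225 + 1)/365.25 = 17.87 PY gives an EAIR of 5.60, above 5.57.

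The reply does not remove the defect. The rule as stated gives wrong limits, and relying on a programmer to depart from it defeats the purpose of specifying it. Loss of terms in the text conversion is an unlikely explanation: the neighbouring EAIR and EAER formulas kept their denominators and factors, both limits lack the same terms, and the text below them defines no exposure.

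**Conclusion.** The concern holds. The limits in SAP 6.1.5.2 are for the count, and nothing elsewhere in the SAP puts them on the EAIR scale. In the Treatment Period tables they are too small by a factor of about 10.9 (bimekizumab) or 21.7 (placebo). With full follow-up and no MAP entry, the factors in the Treatment + SFU tables are 5.4 and 10.8.

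These factors assume 30 and 15 treated participants with complete planned follow-up; early withdrawal or stopping exposure at the first event makes them larger. The values of n are illustrative, but the missing factor itself follows directly from the two formulas.

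The effect is confined to the CI column of the exposure-adjusted TEAE tables. It should be corrected, but it does not bear on the trial's efficacy conclusions.

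**What to change.** In SAP 6.1.5.2, replace the two limits with:

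- LCL = 100 × χ²(2n, α/2) / (2 × ΣT_Exp), with LCL = 0 when n = 0
- UCL = 100 × χ²(2(n+1), 1−α/2) / (2 × ΣT_Exp)

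State that ΣT_Exp is the same sum as in the EAIR denominator, with exposure stopped at the first event, and that it is in years, since SAP 5.6.1 defines time at risk in days. Replace the upper-tail phrase with a statement that the subscripts are lower-tail (cumulative) probabilities. The n = 0 rule is needed because a chi-square quantile with zero degrees of freedom is undefined, and zero counts are plausible for serious events or discontinuations in arms this small.

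The cost is two formula lines and a sentence or two in the SAP, plus a check of the table program. Design and data collection do not change.
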